**Table 2: KIMCL parameters from blood (18mL) and urine (8 mL)**

Hematology (3mL EDTA plasma):		Clinical Chemistry (8mL Li-Hep plasma):
Hemoglobin		Sodium (Na + )
Hematocrit		Potassium (K + )
Erythrocyte count (RBC)		Chloride (Cl  )
Leukocytes (WBC)		Total calcium (Ca 2+ )
Neutrophils, segmented		Phosphate
Lymphocytes		Magnesium (Mg 2+ )
Monocytes		Total bilirubin
Eosinophils		Alkaline phosphatase (AP)
Basophils		Alanine aminotransferase (ALT)
Platelets		Aspartate aminotransferase (AST)
HbaA1 c		γ-glutamyl-transferase (GGT)
Coagulation (3mL sodium citrate)		Urea
International normalized ratio (INR)		Creatinine
Prothrombin time (PZ)		Calcium
Activated partial thromboplastin time (aPTT)		Glucose
Urinalysis (8mL spot urine):		Albumin
Sodium (Na + )		Total protein
Potassium (K + )		Total cholesterol
Chloride		HDL/LDL (Friedewald formula)
Total calcium (Ca 2+ )		Triglycerides
Creatinine		eGFR (CKD EPI equation)
Magnesium		Iron (Fe 2+ )
Phosphate		Transferrin
Protein		Ferritin
Albumin		C-reactive protein
Venous blood (1mL syringe)		Creatine-kinase (CK)
Blood gas analysis		Creatine kinase myoglobin isoform (CK-MB)
Sodium (Na + )		Lactate dehydrogenase (LDH)
Potassium (K + )		hsTroponin T
Chloride (Cl  )		NT-proBNP
Ionized calcium (Ca 2+ ion )		Interleukin-6
Glucose		Coagulation (3mL sodium citrate)

Lactate	
	Von Willebrand factor (vWF)
HbA1 c , glycated hemoglobin A1c; NT-proBNP, n-terminal pro-brain B-type natriuretic peptide, hs, high sensitive.	

### Blood/urine sampling – biobanking

Immediately after collection, 36 mL of blood and 4 mL of spot urine will be transferred to the biobanking facility of the Biobank Graz, located at the Department of the Clinical Institute of Medical and Chemical Laboratory Diagnostics ([name], first floor). A list of stored sampled is provided in **Table 3**. Subjects will be asked to sign the informed consent of the Biobank Graz.

Table 3: Blood and urine samples for biobanking (36mL + 4mL)		
Collected volumes	Aliquoted volumes	Total aliquoted volume (sum)
3x8mL serum	14*235 µL/aliquot 14* 580µL/aliquot	11.410 µL serum
2x6mL EDTA plasma	10*580µL/aliquot 1* 235µL buffy coat/aliquot	5.800 µL EDTA plasma 235µL buffy coat
1x4mL spot urine	4*580 µL/aliquot	2.320 µL spot urine

Analyses of gene mutations that may predispose for the development of heart failure or for cardiovascular risk factors will be analyzed. These analyses will be conducted from buffy coat that will be frozen to -80°C as part of the blood plasma sampling (**see Attachment 3**). An overview on genes to be analyzed is provided in **Table 4**.

Table 4: Genes to be analyzed in genetic testing			
Gene name	Location	Expressed protein	Function of protein
MYBPC3	11.p11.2	Cardiac myosin binding protein C (cardiac MyBP-C)	Cardiac myocyte contractility
TTN	2q31.2	Titin	
MYH7	14q11.2	Myosin heavy chain beta (MHC- $\beta$ )	Myocyte contractility
LMNA	1q22	Lamin A and C	
DES	2q35	Desmin	Cytoskeleton stability
CYP11B2	8q22	Aldosterone synthase	Regulates aldosterone concentration
CaSR	3q21	Calcium sensing receptor	Regulates parathyroid hormone concentration
Analyses of gene mutations that are not currently known to increase the risk of heart failure but may be identified in the future.			

## Echocardiography

Echocardiographic examination will be performed with a Vivid 7 or Vivid 9 (GE Healthcare, Chalfont St Giles, UK). For acquisition of images in the parasternal view the participant will be placed in the steep left-lateral decubitus position. The participant's left arm will be raised. Images will be acquired during quiet respiration. Image rate will be set at least at 70 frames per second. Echocardiographic examination will be outlined in a separate SOP.

## ECG

A 12-lead ECG will be obtained in supine position.

ECG intervals (PR, QRS, QT, QTc), heart rate and pathologies (rhythm abnormalities, AV block, pathological Q, branch block, repolarization abnormalities) will be recorded for each subject.

## Assessment of medical history

Detailed medical history (including dates):

- Any surgery
- Any cardiovascular interventions
- Smoking history (pack years)

- Cardiovascular events: stroke, myocardial infarction (STEMI, NSTEMI), other embolic or thrombotic event, cardiac decompensation, hospitalization for heart failure, peripheral vascular disease
- Cardiovascular disease: arterial hypertension, atrial fibrillation, heart failure signs (ankle edema, elevated jugular venous pulse) and symptoms (NYHA classification, angina pectoris, dizziness, syncope, palpitations)
- Chronic renal failure
- Pulmonary disease (COPD, asthma)
- Any other relevant illness
- Previous fractures?- traumatic/minor injuries/non traumatic
- Previous vertebral trauma
- Previous nephrolithiasis?
- Child-bearing potential? If yes, spot urine pregnancy test will be performed.

### **Assessment of medication history**

Devices or drugs: names (INNs), dosing scheme (if applicable), date and indication of implantation/first prescription of regularly or intermittently taken drugs. Particular care will be taken to ask for treatment of:

1. Heart failure (medical): levosimendane, loop diuretics, ACE-inhibitors, angiotensin II receptor I blockers, mineralocorticoid receptor antagonists, neprilysin inhibitors, beta-blockers, ivabradine, digitalis or digoxin, amiodarone, other
2. Heart failure (devices): ICD, CRT
3. Coronary artery disease: aspirin, PY12 inhibitors, anti-anginal drugs (nitrates or similar)
4. Bone therapy: treatment for osteoporosis including PTH analogues, bisphosphonates, RANKL-antagonists, strontium-ranelate, estrogen receptor antagonists, vitamin D or analogues
5. Others: Pacemaker, oral anticoagulation, heparin, thiazide diuretics, other antihypertensive medication, drugs for psychiatric disorders

## Pregnancy test

Women of child-bearing age will be asked to perform a routine spot urine pregnancy test. If the test result is positive, the participant will not perform X-ray and DXA during visit 2.

## Physical examination

Lung auscultation, heart auscultation, assessment of peripheral edema, assessment of jugular venous pulse height, weight, height, height at 20 years of age. Further examinations will be symptom-oriented.

## Questionnaires

- Minnesota Living with Heart Failure (MLWHF) questionnaires
- SF-36 questionnaire
- Physical Activity Questionnaire (IPAQ)
- Calcium questionnaire (CaQ, 19)
- Pedigree questionnaire

## 24-hours ambulatory blood pressure monitoring (ABPM)

The ABPM device will be attached by a study nurse in the Outpatient Clinic of the Department of Cardiology at Visit 1, before X-ray and after all other procedures of Visit 1 have been performed.

ABPM will be performed using the brachial, oscillometric, automated self-measurement mobil-O-Graph device (I.E.M. GmbH, Stolberg, Germany) with integrated ARCSolver®-Software (Austrian Institute of Technology Wien). The device was validated according to the criteria of the British Hypertension Society (20). The range of measurement is 70–260mmHg for systolic blood pressure, 45–180mmHg for diastolic blood pressure, and 40–240/min for heart rate. Before measurement arm circumferences will be measured and recorded to allow correct choice of cuff size. Measurements of blood pressure and heart rate will be performed every 30 minutes between 22:00h and 6:00h and every 20 minutes between 6:00h and 22:00h. Daytime will be defined as from 09:00 to 21:00, nighttime will be defined as from 01:00 to 06:00 and evening will be defined as from 21:00 to 01:00 according to the ESC position paper 2013 on ambulatory blood pressure monitoring (21). If the ambulatory recordings will be longer than 24 hours, only the first 24 hours will be used for analysis starting the 24 hours timeframe from the first valid recorded measurement. The ARCSolver®-method allows the calculation of PWA values and PWV with each blood pressure measurement.

The ABPM device will be placed on the non-dominant upper arm, except if the office blood pressure measurements reveals more than 20mmHg systolic or more than 10mmHg diastolic difference between the two arms. In that case the arm with the higher blood pressure will be used. The patient

will be instructed on proper handling of the ABPM including resting the arm at the level of the heart during the measurements. Patients will be informed that they should conduct normal daily activities, however they should restrain from strenuous sports.

If less than 70% of the measurements over 24 hours are invalid the ABPM will be considered as unsuccessful and will be redone.

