### **Study aims:**

Aims:

- To quantify the prevalence of osteoporosis in HFrEF (primary aim)
- To quantify the prevalence of vertebral fractures in HFrEF (primary aim)
- To quantify the 24-hour central blood pressure in HFrEF (secondary aim)
- To quantify arterial stiffness in HFrEF (secondary aim)

Exploratory aims:

- To elucidate the role of the bone-vascular axis in HFrEF
  - Relationship between bone metabolism and cardiac systolic function in dependence of vascular status
  - Relationship between bone metabolism and cardiac diastolic function in dependence of vascular status
- To elucidate the role of central arterial pressures and cardiac function in HFrEF
- To elucidate the relationship between arterial stiffness and cardiac stiffness in HFrEF
- To find or apply novel blood- or urine-derived biomarkers that may improve our understanding of mechanisms linking heart and bone pathologies.

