## 10. Statistical analyses

Data will be illustrated by descriptive statistics using numbers and percentages for categorical variables and means and standard deviation or medians and interquartile range for continuous variables, respectively, as appropriate.

To test our primary hypotheses, the correlation between a bone formation marker or central arterial systolic pressure (independent variable, respectively) with LV systolic function (dependent variable) will be analyzed using multivariate linear regression analyses, with adjustment for age, sex, blood lipids, blood glucose, kidney function and other potentially confounding variables.

Differences of echocardiographic and other variables between patients with and without osteoporosis or other categorical variables will be compared using student's t-test, Mann-Whitney U test or analysis of variance (ANOVA), as appropriate. These differences will also be analyzed using multivariate analyses of covariance (ANCOVA), with osteoporosis (yes/no) as fixed factor, echocardiographic or other continuous variables dependent variable and age, sex, blood pressure, blood lipids, blood glucose, kidney function and other potentially confounding variables as covariates. Also other categorical variables of interest and their association with continuous outcome variables will be analyzed in the same manner.

Statistical analyses of the RoC-HF study will be the responsibility of the PIs or persons who received the permission by the PIs to perform statistical analyses. The PIs have published more than 15 original manuscripts in the field of epidemiological research, partly as first authors, and have thus proven their expertise to conduct statistical analyses. Support in statistical analyses will also be provided by [name] or PD [name] who have authored more than 100 peer-reviewed original manuscripts in the field of epidemiological research.

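### The plan does not say how a patient's ambulatory readings become a 24-hour central pressure, and its single 70% validity count can pass a recording with no night data

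*Combined protocol and SAP*

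**What the plan says.** **Schedule.** Section 6d (24-hours ambulatory blood pressure monitoring) takes readings "every 30 minutes between 22:00h and 6:00h and every 20 minutes between 6:00h and 22:00h". The device method "allows the calculation of PWA values and PWV with each blood pressure measurement", so each patient yields a series of central pressures.

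**Aim served.** The Synopsis lists "To quantify the 24-hour central blood pressure in HFrEF (secondary aim"). Section 3 repeats the aim without ranking it.

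**Time frame.** For recordings that run over, "only the first 24 hours will be used for analysis starting the 24 hours timeframe from the first valid recorded measurement".

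**Validity.** "If less than 70% of the measurements over 24 hours are invalid the ABPM will be considered as unsuccessful and will be redone". As printed this is inverted: it fails recordings with few invalid readings. Section 6c (Visit 2) allows one repeat of an unsuccessful recording, with the patient's agreement.

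**Windows.** "Daytime will be defined as from 09:00 to 21:00, nighttime will be defined as from 01:00 to 06:00". A separate evening window covers the four hours between 21:00 and 01:00. The use of these windows is not stated, and 06:00–09:00 falls in none of them.

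**Summary statistics.** Section 10 offers "means and standard deviation or medians and interquartile range for continuous variables". This describes summaries across patients. It does not say how one patient's readings become one value. Elsewhere Section 6d does settle such matters: it says which office readings are averaged, and which tonometry and carotid–femoral velocity recordings are kept.

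**The concern.** A 24-hour pressure is an average over time. When readings are denser by day than by night, an average over readings is a different quantity unless it is weighted. The schedule creates that difference, and the plan gives no rule that resolves it.

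The validity rule adds a second gap. It counts readings without regard to the hour, so a recording can qualify as a 24-hour recording while containing nothing from the night. Weighting cannot repair that, because there is nothing to weight.

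At stake are the secondary 24-hour central pressure estimate and any analysis that uses the 24-hour value. Section 10 names central systolic pressure as an explanatory variable, but does not say whether it comes from ambulatory monitoring or from tonometry. An averaging rule left open until analysis is also a choice that could be made with the data in view.

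**Working it through.** The plan states no reading count, mean, standard deviation (SD) or precision for central pressure, so there is no figure of its own to reproduce.

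**1. Scheduled readings (Section 6d)**

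| Period | Hours | Readings | Share of time | Share of readings |
|---|---|---|---|---|
| 06:00–22:00 | 16 | 16 × 3 = 48 | 66.7% | 75.0% |
| 22:00–06:00 | 8 | 8 × 2 = 16 | 33.3% | 25.0% |
| Total | 24 | 64 | | |

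In the protocol's own windows, day has 12 × 3 = 36 readings, evening 3 + 6 = 9, night 5 × 2 = 10, and the unassigned 06:00–09:00 has 9. These sum to 64.

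**2. What the validity count accepts**

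Reading the rule as at least 70% valid, 0.70 × 64 = 44.8, so 45 readings are needed and 19 may be lost.

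- All 22:00–06:00 readings lost: 48/64 = 75.0%, a pass. With one extra end-point reading, 48/65 = 73.8%, still a pass.
- Night window (01:00–06:00) lost: 54/64 = 84.4%, a pass.
- Evening and night windows both lost: (64 − 19)/64 = 45/64 = 70.3%, a pass.

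The repeat applies only to unsuccessful recordings, so it catches none of these.

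**3. Unweighted mean against time-weighted mean**

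Let D be the 06:00–22:00 mean minus the 22:00–06:00 mean.

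- Complete data: difference = (8/24 − 16/64) × D = D/12.
- No readings from 22:00–06:00: difference = (8/24) × D = D/3.

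The documents give no value for D, so a range is assumed:

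| Assumed D (mmHg) | Complete data | One recording with no night data |
|---|---|---|
| −10 | −0.83 | −3.33 |
| 0 | 0 | 0 |
| 5 | +0.42 | +1.67 |
| 10 | +0.83 | +3.33 |
| 15 | +1.25 | +5.00 |

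**4. Dependence on the choice of windows**

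Suppose instead that a 10 mmHg gap is defined on the protocol's windows (09:00–21:00 against 01:00–06:00), with all other hours halfway between (an assumption). Relative to the daytime level, the 06:00–22:00 mean is lower by 4 × 5/16 = 1.25, and the 22:00–06:00 mean by (3 × 5 + 5 × 10)/8 = 8.125. Then D = 6.875 mmHg, and the two errors are 6.875/12 = 0.57 and 6.875/3 = 2.3 mmHg.

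**5. Effect on the cohort mean**

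If 5% of recordings lacked night data (assumed) and D were 10 mmHg, the cohort mean would move by a further 0.05 × (3.33 − 0.83) = 0.13 mmHg beyond the complete-data shift.

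**6. Effect on a 95% confidence interval**

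Take n = 0.80 × 205 = 164, D = 10 mmHg, bias b = 0.83 and SE = SD/√164. Coverage = Φ(1.96 − b/SE) − Φ(−1.96 − b/SE).

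| Assumed SD (mmHg) | SE | Coverage |
|---|---|---|
| 10 | 0.78 | about 81% |
| 15 | 1.17 | about 89% |
| 20 | 1.56 | about 92% |

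**The case against.** A reader might infer that the plan prescribes a plain mean of readings and therefore overstates 24-hour central pressure. The documents do not support that. Section 10 concerns summaries across patients, and a plain within-patient mean is neither specified nor excluded. The defect is an unstated rule, not a stated wrong one.

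Nor does the error always point upward. The documents give no day–night difference for this population. With no gap there is no error, and with higher pressure at night the sign reverses.

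It is also tempting to treat the D/3 error as an error in the cohort estimate. It belongs to a single recording, and the frequency of such recordings is unknown. The case for a negligible effect is fair as far as it goes: with complete data and a 10 mmHg gap the shift is under 1 mmHg, and less if the gap refers to the protocol's windows. No coverage figure is a result about this trial, because the SD is assumed.

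Read literally, the 70% sentence would reject a recording with 25% invalid readings, so the passes shown above rest on the intended meaning. But the literal rule would also reject a perfect recording, so it cannot be what was meant. Neither reading looks at the time of day.

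Finally, the cited position paper or the device software may contain averaging or validity rules. That cannot be judged from the documents. If such rules are meant to apply, the plan should state them.

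What remains after all this is that the averaging rule is missing and that the validity count can admit recordings without night data.

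**Conclusion.** The point stands as a gap in specification together with a validity rule that ignores the time of day. The reading counts and pass percentages follow from the protocol's schedule, given the intended reading of the 70% rule.

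The size is conditional. If an unweighted mean is used, the shift is 1/12 of the day–night gap with complete data and 1/3 of it in a recording with no night readings. Its direction follows the sign of the gap. The complete-data shift would not shrink with more patients, but it is modest. The missing-night case is larger per recording, and its effect on the cohort is unknown. The gaps, the SD, the number analysed and the frequency of night loss are all assumptions.

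Only the secondary 24-hour central pressure aim and analyses that use that value are touched. The osteoporosis and vertebral fracture prevalence aims and the sample size are not. The change is inexpensive and worth making before analysis.

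**What to change.** Amend the ambulatory monitoring section, with a matching line in Section 10:

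1. Define 24-hour central pressure as a time-weighted mean, for example the average of hourly means, and say what is done when an hour has no valid reading. A simpler form is 2/3 × mean(06:00–22:00) + 1/3 × mean(22:00–06:00).
2. Correct the 70% sentence so that at least 70% of readings must be valid.
3. Require a minimum share of valid readings separately in the day and night sampling periods before a recording counts toward the 24-hour value. Using 70% in each would mean 34 of 48 by day (0.70 × 48 = 33.6) and 12 of 16 by night (0.70 × 16 = 11.2).
4. State how these sampling periods relate to the 09:00–21:00, 21:00–01:00 and 01:00–06:00 windows, and assign 06:00–09:00 or say that it is unused in window summaries.
5. Report how many recordings fail the night minimum.

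The cost is a few sentences and a small change to the analysis code. Some recordings with poor night data will become unsuccessful. Because the repeat is allowed once and only with the patient's agreement, some of these will end up missing. Their number cannot be estimated from the documents.

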5. ECG
6. Echocardiography
7. Spot urine pregnancy test for women of child-bearing age
8. 24-hours ambulatory blood pressure monitoring (ABPM).

9. Scheduling of visit 2, at least 2 days after visit 1 to facilitate performance of 24-hours ABPM. The patient will be advised to remove and switch off the ABPM device 24 hours after attaching. The patient will be advised to attend visit 2 as fasting and non-smoking over the preceding night.

## Visit 2

Visit 2 will take place at least 2 days after visit 1 to facilitate performance of 24-hours ABPM. Visit 2 will take place in the Clinical Studies Outpatient Clinic of the Department of Cardiology. The participant should be fasting and should not have smoked over the previous night. Following study procedures will be performed:

1. X-ray of the thoracic and lumbar spine. Women of child-bearing age will not perform X-ray in case of a positive pregnancy test during visit 1.
2. Re-obtainment of ABPM device. If ABPM was unsuccessful it can be repeated once, if the patient agrees.
3. Vital signs (office blood pressure and heart rate)
4. Hand Grip
5. 4m Gait Speed
6. Sampling of blood (65 mL) and spot urine (12 mL)

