### **PWA**

The pulse wave analysis (PWA) will be performed using the SphygmoCor® (AtCor Medical, Sydney, Australia), which allows a noninvasive central blood pressure assessment. The patient will have to lie in a supine position for 15 minutes before the start of the measurements and care will be taken to assure a quite environment. Initially the brachial blood pressure will be recorded in supine position and the SphygmoCor® will be calibrated using this measurement. Using the technique of the radial applanation tonometry the pulse wave analysis will be performed with the SphygmoCor® to measure at least two PWA recordings. Only recordings with a quality index above 80% will be accepted and otherwise the measurements will have to be repeated. If there are major differences between the parameters, such as an augmentation index difference of more than 4%, a third measurement will be done. The PWA results in which the measured values are closer to each other will be used.

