## 9. Sample size calculation

The sample size calculation of RoC-HF is based on data from previous analyses that reported prevalence data of osteoporosis among patients with HFrEF leading to an expected prevalence of osteoporosis in RoC-HF of 20%. Osteoporosis is defined as a T-Score < -2.5 (measured by DXA), and severe osteoporosis is defined as a T-Score < -2.5 and presence of a fragility fracture, e.g., a vertebral fracture. In most of available studies on patients with HFrEF, data from DXA scans were not available. Therefore, presence of a vertebral fracture was commonly used as a criterion of osteoporosis. Thus, these studies likely underestimated the real prevalence of osteoporosis, because presence of a fracture may constitute only the "tip of the iceberg". Taken together, previous studies reported on prevalences of osteoporosis of 12 – 16% (see **Table 6**).

Table 6: Prevalence of osteoporosis as reported in previous heart failure cohorts				
Study	Patient number	Heart failure definition	LVEF in %	Data
Lyons et al (30)	623	Listed for transplant	32 +/- 16	12% with vertebral fractures
Mazziotti et al (31)	1031 (430 vs 601 healthy controls)	ICD + revision of clinical records	27 (15-45)	16.1% with vertebral fracture
Youn et al (32)	65	Acute decompensated heart failure	28 +/- 12 (males) 36 +/- 16 (females)	15% with T-Score < -2.5

Given that the RoC-HF study procedures comprise DXA scan as well as X-ray of both the thoracic and lumbar spine, we expect a prevalence of osteoporosis in RoC-HF of 20 % (95% confidence interval: 14 -26). Calculating with a significance level of 5% and a two-sided P-value leads to a number of 171

participants to be analyzed. Calculating with 20% unavailable data due to invalid ABPM, missing laboratory values or other missing parameters, we will need to enroll 205 subjects in total.

Support in sample size calculation was provided by the Institute for Medical Informatics, Statistics and Documentation of the Medical University of Graz ([name]).

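### The ABPM validity rule is reversed as written: it fails recordings with 20 to 64 valid readings out of 64 and lets through those with 0 to 19

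*Combined protocol and SAP*

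**What the plan says.** Section 6d (ABPM) sets the reading schedule as "every 30 minutes between 22:00h and 6:00h and every 20 minutes between 6:00h and 22:00h". It says that the device software "allows the calculation of PWA values and PWV with each blood pressure measurement", so each cuff reading can also yield central haemodynamic values. The section closes with the validity rule: "If less than 70% of the measurements over 24 hours are invalid the ABPM will be considered as unsuccessful and will be redone".

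Three other places bear on it:

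- **Section 6c, Visit 2, item 2** uses the term without defining it: "If ABPM was unsuccessful it can be repeated once, if the patient agrees".
- **Section 9 (sample size), repeated in the sample size paragraph of the Introduction,** lists failed ABPM among the reasons for the missing-data allowance, without a threshold: "Calculating with 20% unavailable data due to invalid ABPM, missing laboratory values or other missing parameters".
- **The synopsis** lists 24-hour central blood pressure in HFrEF as a secondary aim. Section 3 lists the same aim.

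**The concern.** The condition points the wrong way. A recording is declared a failure when the share of *invalid* readings is *below* 70%. A recording with no invalid readings meets that condition, and one with 70% or more invalid readings does not. Nothing elsewhere in the document supplies a threshold that would override the sentence.

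The rule decides which recordings have to be repeated. It plausibly also decides which ones count as usable for the 24-hour central pressure aim, and what section 9 means by failed ABPM in its 20% allowance. ABPM is the only 24-hour pressure measurement in the protocol. The SphygmoCor assessment, "which allows a noninvasive central blood pressure assessment", is taken supine at a visit and cannot stand in for it.

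If the intended cut-off is not written down, study staff deciding on a repeat at Visit 2 and an analyst deciding on exclusions may apply different ones. The analyst could also choose a cut-off after seeing the data.

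**Working it through.** The protocol gives no count of readings, so there is no stated figure to reproduce. The count below is derived from the schedule in section 6d (ABPM).

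**Scheduled readings in 24 hours**

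- 06:00 to 22:00: 16 h × 3 per hour = 48
- 22:00 to 06:00: 8 h × 2 per hour = 16
- Total: 48 + 16 = 64
- 70% of 64 = 0.70 × 64 = 44.8. This is not a whole number, so no recording falls exactly on the boundary.

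**Each reading of the rule, with v valid readings and 64 − v invalid**

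| Reading of the rule | Fails when | Fails (valid readings) | Passes (valid readings) |
|---|---|---|---|
| As written: less than 70% invalid | 64 − v ≤ 44 | 20 to 64 | 0 to 19 |
| *invalid* changed to *valid*: less than 70% valid | v ≤ 44 | 0 to 44 | 45 to 64 |
| *less* changed to *more*: more than 70% invalid | 64 − v ≥ 45 | 0 to 19 | 20 to 64 |

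**Where the two corrections differ**

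They give opposite verdicts for v = 20 to 44, which is 25 possible counts, from 20/64 = 31% to 44/64 = 69% valid. The rule as written and the first correction agree only in that same range, where both fail the recording. They are opposed from 0 to 19 and from 45 to 64. The rule as written and the second correction are opposed at every count.

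**Sensitivity to the denominator**

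If the readings at both ends of the 24 hours are counted, the total is 65 and 70% is 45.5. The rule as written then fails 20 to 65 valid and still passes 0 to 19. The first correction needs 46 valid and the second still needs 20. The reversal itself needs no denominator, because a recording with 0% invalid readings fails under any count.

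**Link to the sample size**

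The allowance in section 9 is 205 − 171 = 34 participants for missing data of all kinds. The documents do not say how many of the 34 are expected to come from ABPM, so no effect on that figure can be calculated.

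**The case against.** The strongest reply is that this is an obvious slip. No one would repeat a perfect recording, so the literal rule is unlikely to be applied and the counts of 20 to 64 and 0 to 19 describe a harm that will not occur. On this view the remaining problem is modest:

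- The aim affected is secondary.
- The 171 is sized on osteoporosis prevalence, not on ABPM.
- The documents do not show how many participants would have 20 to 44 valid readings.
- The sentence speaks only of repeating the recording, so accepting or excluding data is an inference from it.
- The figure of 64, and scheduled rather than attempted readings as the base, are also inferences.

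Much of this stands. The literal rule is probably not what staff will follow, the practical effect cannot be quantified, and the counts depend on a scheduled denominator. It does not dispose of the point, because recognising the slip does not show which threshold was intended. The two natural corrections differ over 25 possible counts, and those are the borderline recordings that a validity rule exists to settle. One indirect hint favours the stricter correction: the PWA part of section 6d accepts only recordings with a quality index above 80%. That is a different device and a different measure, so it does not settle the matter.

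The difference between section 6d, where a failed recording is to be redone, and section 6c, where one repeat is optional, can be read as a rule and its qualification. It is not counted here as an error.

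**Conclusion.** The concern holds. The only definition of a failed ABPM is wrong as written and should be corrected. On 64 scheduled readings, it fails 20 to 64 valid and by implication accepts 0 to 19. The two plausible corrections set the pass mark at 45 or at 20 valid readings, and the documents do not choose between them.

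The consequence is limited to the repeat decision and, plausibly, to which recordings are usable for the secondary aim on 24-hour central pressure and are counted as failed in the 20% allowance. No primary aim depends on it. The regression on central systolic pressure in section 10 might be affected. That is not established, because section 10 does not say whether the pressure comes from ABPM or from SphygmoCor.

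The counts assume that the denominator is the number of scheduled readings and that readings follow the stated intervals. The reversal assumes neither.

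**What to change.** The sponsor should first confirm the intended threshold and whether the denominator is scheduled or attempted readings, and then correct the sentence in section 6d. Suggested text, if this is the intent: *An ABPM recording is unsuccessful if fewer than 70% of its scheduled 24-hour readings are valid.* That requires at least 45 of 64 valid readings to pass.

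The same edit can make the repeat provision in section 6d match the single optional repeat in section 6c, Visit 2, item 2.

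The cost is a one-sentence amendment, with no added procedures or participants.

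Separately, and not as an error in the plan, the sponsor may wish to consider a night-time minimum. A pooled 70% threshold can be met with no valid reading from 22:00 to 06:00 (48/64 = 75%). The protocol already has a window for this, "nighttime will be defined as from 01:00 to 06:00", with 5 h × 2 = 10 scheduled readings. The documents do not allow the cost of such a minimum to be estimated.
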